6.4.3 Mepolizumab administration at 300 mg (Visits 11 to 13)

Visits 11 to 13 will be scheduled 28 days (± 7 days) from the prior visit. These visits may be performed remotely if needed due to COVID-19 restrictions and difficulties with travel. In such cases, the pharmacy will provide autoinjectors for SC mepolizumab administration.

The following procedures and laboratory tests will be performed:

- Targeted history and physical examination, including limb measurements. If the visit is conducted remotely, a targeted history and physical examination will be conducted virtually.
- Vital signs, including weight. The subject will measure and report their weight and temperature if the visit is performed remotely.
- Review of symptom/weight logs and patient-reported outcome measures adherence
- CBC with differential
- Pregnancy test (females of childbearing potential; not performed at a remote visit)
- AE assessment

Following completion of the evaluation and pregnancy test (if applicable), mepolizumab 300 mg SC will be administered.

6.4.4 End of de-escalation phase (Visit 14)

The end of study visit for subjects in the Dose De-escalation Phase will be scheduled 28 days (± 7 days) after Visit 13.

The following procedures and laboratory tests will be performed:

- Targeted history and physical examination, including limb measurements
- Vital signs, including weight
- CBC with differential
- Routine laboratory testing, including acute care, hepatic, and mineral panels, LDH, CPK, CRP, and urinalysis
- Serum tryptase, aldolase, and quantitative immunoglobulin levels (including IgE)
- Collection of serum or plasma and urine for immunologic analyses and quantification of eosinophil granule proteins
- Collection of whole blood for isolation and storage of plasma and cells for research studies
- Whole blood lymphocyte phenotyping (TBNK) and RNAseq
- AE assessment

After this visit, participation of subjects in the Dose De-escalation Phase will be complete.

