4.3 Subject Inclusion Criteria

A subject will be eligible for participation in the study only if all of the following criteria apply:

- 1) The subject is male or female, aged 18 years or older.
- 2) The subject has a documented diagnosis of EAE.
- 3) The subject has symptoms of EAE in the cycle prior to screening, including but not limited to fever, swelling, hives or rashes, weight gain, muscle pain, and lymphadenopathy.
- 4) Cycling of eosinophils is ongoing as indicated by a peak AEC $\geq 1500/\text{mm}^3$ during at least one cycle in the prior 3 months.
- 5) If taking corticosteroids ≤ 40 mg daily, the subject is able and willing to stay on a stable dose for 6 weeks prior to screening.
- 6) The subject agrees to storage of study samples.

- 7) The subject is able to provide informed consent.
- 8) Females are eligible for this study if they are:
 - i. of non-childbearing potential (i.e., women who have had a hysterectomy or tubal ligation or are postmenopausal as defined by no menses in 1 year); OR
 - ii. of childbearing potential but willing to practice effective contraception or abstinence during administration of the study drug and for 100 days (5 terminal half-lives) after administration of the study drug.
 - iii. Not breastfeeding.

Participation of Women:

Pregnancy: The effects of mepolizumab on the developing human fetus are unknown. For this reason, women of childbearing potential must agree to use adequate contraception (see below for acceptable methods) prior to study entry, for the duration of study participation, and for >5 terminal half-lives (approximately 100 days) after administration of the last dose of study drug. Non-reproductive potential is defined as post-menopausal, male partner who has azoospermia or is surgically sterile (at least 6 weeks before screening) and is the sole sexual partner, surgical sterility, or a congenital or acquired condition that definitely prevents conception. Further, postmenopausal is defined as at least 12 consecutive months with no menses at age 50 or older, or a high follicle-stimulating hormone level in the postmenopausal range at ages 45-50 years in subjects not using hormonal contraception or hormone replacement therapy.

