Females with reproductive potential must either practice complete and uninterrupted abstinence from heterosexual activity or use 2 of the following methods of contraception with their partners. The 2 methods must include either 2 barrier methods, or 1 barrier method and 1 non-barrier method, both of which must be consistently used:

Barrier Methods:

- 1) Diaphragm with spermicide
- 2) Cervical cap with spermicide or contraceptive sponge (for nulliparous subjects only)
- 3) Male or female condom (cannot be used together)

Non-Barrier Methods

- 1) An intrauterine device with a documented failure rate of <1%

- 2) Hormonal contraception: pill (estrogen/progestin or progestin-only), patch, vaginal ring, rod implanted in the skin, or subcutaneous injection methods

Females of childbearing-potential must have a negative pregnancy test result prior to receiving mepolizumab at each on-site study visit. During the course of the study, if a woman becomes pregnant or suspects she is pregnant, she should inform the study staff and her primary care physician immediately. Subjects who become pregnant will be entered into the mepolizumab pregnancy registry.

Fertility: There is no fertility data in humans. Animal studies showed no adverse effects of anti-IL-5 treatment on fertility.

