6.3.6 Completion of primary and secondary endpoint assessments (Visit 8)

Visit 8 will again be scheduled 28 days (± 7 days) after Visit 7. This visit may occur over several days.

The following procedures and laboratory tests will be performed:

- Targeted history and physical examination, including limb measurements
- Vital signs, including weight
- CBC with differential
- Routine laboratory testing, including acute care, hepatic, and mineral panels, CRP, and urinalysis
- Serum tryptase, aldolase, and quantitative immunoglobulin levels (including IgE)
- Collection of serum or plasma and urine for immunologic analyses and quantification of eosinophil granule proteins
- Collection of whole blood for isolation and storage of plasma and cells for research studies
- Whole blood lymphocyte phenotyping (TBNK) and RNAseq
- Optional bone marrow biopsy and aspiration, requested of subjects for whom a sample was collected/available prior to study treatment (may be done once at any time while on study drug)
- AE assessment

After completion of the procedures described above, subjects who have received benefit from mepolizumab administration will begin the Dose De-escalation Phase (Visits 8-14, as outlined in section [6.4](#)).

For subjects who do not participate in the Dose De-escalation Phase, Visit 8 will be the end of study visit.

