6.8 Recontact of Subjects After Trial Termination

Subjects will not be recontacted on this study after trial termination. Subjects will remain on the screening protocol 94-I-0079 on which they may be recontacted if there are important findings that result from this study.

7. Study Procedures/Evaluations

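### Scheduled collection of new pregnancies and AEs stops about 28 days after the last dose, while the protocol's contraception requirement runs to about 100 days

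*Combined protocol and SAP*

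**What the plan says.** **Contraception window.** Section 4.3 asks women of childbearing potential to use contraception or abstain during dosing and "for 100 days (5 terminal half-lives) after administration of the study drug". The paragraph on participation of women counts this from the final administration ("approximately 100 days) after administration of the last dose of study drug") and gives the unknown fetal effects as the reason.

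**End of participation.** For de-escalation subjects, section 6.4.4 states: "The end of study visit for subjects in the Dose De-escalation Phase will be scheduled 28 days" (±7) after Visit 13, and then: "After this visit, participation of subjects in the Dose De-escalation Phase will be complete". For the others, section 6.3.6 states: "For subjects who do not participate in the Dose De-escalation Phase, Visit 8 will be the end of study visit". Visit 8 falls 28 (±7) days after Visit 7, which is their last dose.

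**After the last visit.** Section 12.2 elicits AEs whenever there is contact with the subject. Section 12.4 carries forward only AEs still unresolved when follow-up ends. Section 6.8 says: "Subjects will not be recontacted on this study after trial termination". It adds that subjects remain on 94-I-0079, where they may be contacted about important findings. Sections 6.7 and 12.3 provide for registry entry and follow-up on 94-I-0079 once a pregnancy on study is known.

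**Pregnancy tests.** Under section 4.3, women of childbearing potential "must have a negative pregnancy test result prior to receiving mepolizumab at each on-site study visit". For Visits 11 to 13, section 6.4.3 lists "Pregnancy test (females of childbearing potential; not performed at a remote visit"; section 6.4.2 has the same exception for Visits 9 and 10. The list in 6.4.4 for Visit 14 has no test. At Visit 8 the test appears only in 6.4.1, for subjects about to start de-escalation.

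**The concern.** By equating 100 days with five terminal half-lives, the protocol ties its contraception requirement to residual drug. Scheduled follow-up stops at 1.4 of those five half-lives. A pregnancy that begins, or an AE that starts, between the last visit and day 100 would reach the trial only if the subject or the 94-I-0079 team happened to report it.

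The safety summary in section 15.2 sets no cut-off for AEs, so a reader of the results could not tell whether a lack of late events means that none occurred or that nobody asked. The planned sample is 12 subjects, section 1.1.2 reports no published use of the drug in EAE, and the starting dose is above the approved one. One missed pregnancy or serious event would matter.

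**Working it through.** **Inputs.** Visit 4 is Day 15 and Visit 6 is 28 days later (section 6.3.4, Table 1). Each later visit adds 28 days, with ±7 at Visits 8 to 14. The post-dose window is 100 days, or five half-lives (section 4.3).

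**1. Reproduce the schedule.** 15 + 28 = 43 (Visit 6), then 71 (Visit 7), 99 (Visit 8), 127, 155, 183, 211, 239 (Visit 13) and 267 (Visit 14). These match Tables 1 and 2.

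**2. Days after the last visit.** With the last visit f days after the last dose, the uncovered part of the window is 100 − f:

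| f (days) | Uncovered days | Share of the 100 days |
|---|---|---|
| 21 | 79 | 79% |
| 28 | 72 | 72% |
| 35 | 65 | 65% |

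The window closes on Day 71 + 100 = 171 for subjects who stop at Visit 8, and on Day 239 + 100 = 339 for de-escalation subjects.

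**3. Other denominators.** Counted from first dose (Day 15) to last dose plus 100 days, the uncovered share is 72/(171 − 15) = 72/156 = 46% (42% to 51%) for subjects who stop at Visit 8. For de-escalation subjects it is 72/(339 − 15) = 72/324 = 22% (20% to 24%).

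**4. Residual drug.** The implied half-life is 100/5 = 20 days. Assuming mono-exponential decay, the fraction left at day 28 is 2^(−28/20) = 0.379, or about 38% (30% to 48% for f = 35 to 21). The share of day 0–100 exposure that falls after day 28 is (2^(−1.4) − 2^(−5))/(1 − 2^(−5)) = (0.379 − 0.031)/0.969 = 36% (27% to 47%).

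**5. Last listed pregnancy test.** Visit 8 dosing takes place in the Day Hospital, so that test is done on site. If Visits 9 to 13 are all remote, the last listed test is on Day 99, and 239 − 99 = 140 days pass before the last dose. Section 6.4.2 asks for Visit 10 at NIH if feasible. If that is the last on-site visit, the gap is 239 − 155 = 84 days.

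**6. Tests after the last dose.** The section 6 lists contain none for either group. The extracted Table 1 row is broken and shows five marks against the four primary-phase visits in section 6 (1, 4, 6 and 7). A mark at Visit 8 or the unscheduled visit therefore cannot be ruled out. The footnote ties the test to dosing, and this point rests on the section 6 lists.

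**The case against.** The strongest reply is that no two passages collide. The 100 days is a contraception rule for women of childbearing potential. Nothing makes it an AE-reporting window, so applying it to all subjects and all AEs is a preference for longer follow-up. This is right as far as it goes: the protocol has left the end date for new events undefined, and the proposal fills that gap with the only post-dose interval the protocol itself supplies.

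There is also a backstop. Subjects remain on 94-I-0079, women are told to report a pregnancy, and a known pregnancy is entered in the registry and followed to delivery or termination. That stands, and a reader who inferred that late pregnancies have no route to the registry would go too far. But the backstop is passive: section 6.8 describes contact there for important findings and does not mention soliciting new events for this trial. Section 6.8 also speaks of the end of the trial, which need not be a given subject's last visit. Section 6.4.4, however, ends the subject's own participation at Visit 14.

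On remote testing, the rule in 4.3 is limited to on-site visits, so the remote lists do not literally breach it. The gap is that dosing may take place remotely and the rule does not address that case. The 140-day figure is the extreme, since in-person Visits 9 and 10 are preferred.

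**Conclusion.** The point holds as a gap in scheduled ascertainment that is cheap to close. About 72 (65 to 79) of the 100 days after the last dose have no scheduled active collection of new pregnancies or AEs. In the worst case the last listed pregnancy test precedes the last dose by 140 days. The day counts rest only on the protocol's 28-day schedule and its 100-day figure; the residual-drug figures also assume first-order decay.

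Two stronger readings are not supported:

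- A reader might infer that most of the at-risk period is unobserved. That is true only of calendar days in the post-dose window. It is 22% to 46% counted from first dose, and about 36% of the 0–100 day window when weighted by exposure.
- A reader might infer that a rebound flare during washout would be missed. The documents nowhere mention rebound. Those who complete the primary phase and stop at Visit 8 are subjects without investigator-judged benefit, and responders may continue mepolizumab after the study (sections 3.1 and 5.4), so for some there may be no washout.

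**What to change.** Reconcile sections 4.3, 6.3.6, 6.4.4, 6.7, 6.8 and 12.4 so that they state one end date for new pregnancies and AEs:

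- Keep reporting open until 100 days after each subject's last dose.
- Add one REDCap or telephone contact at that point: about Day 171 for subjects who stop at Visit 8, and about Day 339 for de-escalation subjects.
- State whether these data are collected under this protocol or under 94-I-0079 and, if the latter, how they enter this trial's safety summary.
- Flag events that occur under post-study mepolizumab, so that they are not read as events off drug.

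Separately, reconcile the pre-dose test rule in 4.3 with the remote-visit lists in 6.4.2 and 6.4.3, and check the pregnancy-test rows of Tables 1 and 2 against section 6. Which testing rule applies at remote dosing is for the sponsor to decide.

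The cost is one remote contact per subject, changes to protocol and consent wording, and last-subject close-out about 72 days (72/7, or about 10 weeks) later.

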6.5 Unscheduled Visit

Extra visits may be scheduled in between any of the scheduled visits due to need to re-evaluate the subject or conduct additional studies for clinical care of the subject.

6.6 Early Termination Visit

Subjects who desire to withdraw from study and further administration will be brought back for an early termination visit and clinical assessment. The principal investigator may also elect to terminate participation of the subject from the study for lack of adherence to study visits (according to the withdrawal criteria in section 12.8), safety (pausing or halting rules as described in sections 12.5 and 12.6), or lack of efficacy. Reasons for withdrawal and safety labs will be captured during this visit.

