1.1 Background Information

EAE, also known as Gleich's Syndrome, is characterized by recurrent episodes of urticaria, fever, angioedema, weight gain, and dramatic eosinophilia that occur at 3- to 6-week intervals and resolve with spontaneous diuresis in the absence of therapy (1). The dramatic waxing and waning of clinical manifestations, which can include shifts in weight of up to 40 pounds, has a significant impact on the lives of patients with EAE. Although conventional HES therapies, including glucocorticoids, are effective in reducing symptoms, the toxicity of these therapies limits their long-term use in EAE.

EAE is an extremely rare disorder. Among 303 consecutively enrolled subjects on our natural history protocol studying eosinophilic syndromes (94-I-0079), 12 subjects with EAE were identified. The estimated prevalence of HES is 0.036/100,000 persons based on coding in the SEER (Surveillance, Epidemiology, and End Results Program) database, although this is likely underestimated due to the lack of specific International Classification of Diseases codes for HES (2). Assuming that the proportion of referrals to NIH for EAE reflects the proportion of such patients in the general HES population, the prevalence of EAE is estimated to be 0.012-0.2/100,000 persons in the United States. This low prevalence has precluded clinical treatment studies in EAE to date.

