For the SC formulation: Mepolizumab administration will occur via an autoinjector and will be given by the subject or a caregiver as multiple injections of 100-mg each. Each injection should be given into the thigh or abdomen (avoiding the 5 cm [2 inches] around the navel) when given by the subject or caregiver; the upper arm may be used if the injection is administered by a caregiver. Each injection site should be separated by at least 5 cm (2 inches). Injections should not be administered into areas of skin that are tender, bruised, red, or hard. If a dose is missed, it should be administered as soon as possible. Thereafter, the subject should resume dosing on the usual day of administration. If the next dose is already due, then it should be administered as planned.

Dose Adjustments/Modifications/Delays

During the Primary Study Phase administering mepolizumab at 700 mg IV, the dose will remain the same without modification unless held or stopped due to a

pause (section 12.5), halt (section 12.6), or withdrawal of the subject (section 12.8). During the Dose De-escalation Phase, the dose will be reduced as outlined in the protocol unless held or stopped due to a pause, halt, or withdrawal of the subject.

Duration of Therapy

A total of 3 doses of 700 mg IV will be given on this protocol over a 3-month duration for all subjects; subjects in the Dose De-escalation Phase will have 6 months of additional de-escalating doses at 500 mg (3 doses) and 300 mg (3 doses). The total duration of therapy for participation in both the Primary Study Phase and the Dose De-escalation Phase will be 9 months.

Tracking of Dose

A record of the number of doses and lots used will be kept in the pharmacy for doses administered in-person at the NIH Clinical Center Day Hospital. For remote visits during the Dose De-escalation Phase, subjects will either have an observed administration via telehealth or will log the dose on a dose tracker.

Limitations on Prior Therapy

Subjects who have received mepolizumab within 6 months or 5 half-lives (whichever is longer) will not be eligible for this protocol.

Use of Ancillary Medications/Over-the-Counter Products/Foods

Only corticosteroids will be permitted for treatment in addition to mepolizumab. There are no restrictions on use of other prescribed medications, over-the-counter products or foods.

Subject Access to Study Agent After End of Study Assessments

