6.1 Enrollment (Visit 1)

Screening of subjects for this study will occur under NIH protocol 94-I-0079 (“Eosinophil activation and function in parasitic infections and other conditions with increased tissue or peripheral blood eosinophilia in humans”).

Subjects with EAE will be brought in for enrollment (Visit 1). Visit 1 may occur over several days.

After signed informed consent is obtained, the following procedures and laboratory tests will be performed:

- Complete history and physical examination, including limb measurements
- Vital signs, including weight
- Photography (with infrared thermography if available)
- CBC with differential
- Routine laboratory testing, including acute care panel, hepatic panel, mineral panel, lactate dehydrogenase (LDH), creatine kinase (CPK), C-reactive protein (CRP), and urinalysis

- Serum tryptase, aldolase, and quantitative immunoglobulin levels (including IgE)
- Urine pregnancy test (females of childbearing potential only)
- Collection of serum or plasma and urine for immunologic analyses and quantification of eosinophil granule proteins
- Collection of whole blood for isolation and storage of plasma and cells for research studies
- Whole blood lymphocyte phenotyping by T-, B-, and natural killer-cell analysis (TBNK) and RNA sequencing (RNAseq)
- Optional bone marrow biopsy and aspiration, if not available under protocol 94-I-0079 or another NIH protocol
- Optional skin punch biopsy
- AE assessment

The subjects will start a log of symptoms of EAE that they will fill out daily to track symptoms, weight, and temperature. They will also start daily and monthly patient-reported outcome measures for angioedema symptoms and quality of life at this time. These logs and measures will be completed electronically using REDCap. Subjects will discontinue daily logs and measures after the third mepolizumab visit (Visit 7) but will continue monthly measures through the end of the primary study phase (section [7.1.2](#)).

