7.1.3 Symptom Logs and Patient-reported Outcomes

Patients will fill out a daily log capturing symptoms, weight, and temperature (Appendix E: Patient Symptom Log), and fill out validated patient-reported outcome measures for angioedema (daily) and quality of life (monthly; questionnaires provided as [Appendix G](#)). These logs and measures will be completed electronically using REDCap. Subjects will also be encouraged to notify the investigators of any new signs or symptoms that develop between study visits. The daily logs and measures will be completed through the end of study endpoint assessments (Visit 8). For subjects in the de-escalation phase, after Visit 8 until study completion, weekly angioedema and monthly quality of life questionnaires will be continued, and weekly symptoms logs ([Appendix F](#)) will be completed.

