12.8 Withdrawal Criteria for an Individual Subject

A study subject will be withdrawn for any of the following:

- An individual subject's decision. (The investigator should attempt to determine the reason for the subject's decision.)
- Non-compliance with study procedures (e.g., changing corticosteroid doses without principal investigator discretion, inability to comply with study visits) to the extent that it is potentially harmful to the subject or to the integrity of the study data.
- Any clinical AE, laboratory abnormality, intercurrent illness, other medical condition or situation that occurs such that continued participation in the study would not be in the best interest of the subject.
- The investigator determines that continued participation in the study would not be in the best interest of the participant.
- A change in the subject's baseline condition after enrollment so that the subject no longer meets the following eligibility criteria:
 - Development of pregnancy.
 - Development of a new malignancy (with the exception of localized skin cancer [basal or squamous] that may be cured by resection).
 - Withdrawal of permission for storage of study samples.
 - Permanent loss of decision-making capacity to provide informed consent.

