Key: AE- adverse event; AEC- absolute eosinophil count; ANC- absolute neutrophil count; CBC- complete blood count; CPK- creatine kinase; IgE- immunoglobulin E; LDH- lactate dehydrogenase; PBMC- peripheral blood mononuclear cell; PROs- patient-reported outcome measures; TBNK- T, B, and natural killer cell; UV- unscheduled visits; ¹ Study visits may be rescheduled or study procedures may be waived or modified to be performed remotely due to travel limitations or safety concerns during the coronavirus disease 2019 pandemic (as described in protocol section 6); ² All subjects will complete Visit 8. Subjects who experienced benefit from mepolizumab administration will continue in the de-escalation phase (which begins with additional procedures at Visit 8—see Table 2 below); for subjects who do not continue in the de-escalation phase, Visit 8 will be the final study visit. ³ The exact timing of Visit 1 through Visit 5 may vary from this schedule based on subject cycle times. Visits 2 and 3 may be combined if neutrophils and eosinophils peak <1 week apart. Every effort will be made to schedule Visit 5 in advance of Visit 6; in the event that Visit 5 occurs within 1 day of Visit 6, only collection of whole blood for storage will be performed for Visit 5. Visits 6, 7, and 8 will be scheduled monthly based on the timing of Visit 4. ⁴ Urine pregnancy test prior to administration of mepolizumab in women of child-bearing potential; ⁵ Performed electronically via REDCap. Symptom logs to be performed daily; PROs daily and monthly, not only at study visits; daily symptom logs and measures will be discontinued after Visit 7, and monthly questionnaires will be continued through Visit 8; ⁶ Home labs will be done 2-3X/week, depending on subject cycle times (2X/week in some cases or after peak is obtained); ⁷ Optional. Bone marrow will be requested to be performed only once at Visit 1 or 2, if a sample is not available from another NIH protocol. Skin punch biopsy will be requested to be performed only once on Visits 1, 2, or 3; ⁸ May be requested once at any time while on study drug if a pre-treatment sample was collected/available.

Table 2. Schedule of Procedures/Evaluations for the De-escalation Phase.

Evaluations	Study Drug 500 mg	Study Drug 500 mg	Study Drug 500 mg	Study Drug 300 mg	End of De-escalation	UV			
Visit Number	8	9	10	11	12	13	14		
Day (assuming 4-week cycle)	Day 99	Day 127	Day 155	Day 183	Day 211	Day 239	Day 267		
Window (days)	±7	±7	±7	±7	±7	±7	±7		

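### Section 6.6 allows a treated subject to be taken off study for lack of efficacy before Visit 8 and nothing continues the symptom log, so the average percent reduction can be modestly overstated if response varies

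*Combined protocol and SAP*

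**What the plan says.** Section 6.6 gives three grounds on which the principal investigator may end participation in the study. Non-adherence is tied to 12.8 and safety to 12.5 and 12.6. The third, "or lack of efficacy. Reasons for withdrawal and safety labs will be captured during this visit", has no cross-reference, criterion or earliest time.

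The expected path is three 700 mg doses and then Visit 8 for everyone (3.1, 5.4). Table 1 in Appendix B says "All subjects will complete Visit 8", and 6.3.6 says "For subjects who do not participate in the Dose De-escalation Phase, Visit 8 will be the end of study visit". Section 5.4 nevertheless lets the 700 mg dose be held or stopped through a "pause (section 12.5), halt (section 12.6), or withdrawal of the subject (section 12.8"), and one ground in 12.8 is "The investigator determines that continued participation in the study would not be in the best interest of the participant".

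A subject who does not resume study agent is followed for safety (12.5.2.1, 12.6.2.1). Only subjects withdrawn before the first dose are replaced (12.8.1).

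The protocol disagrees on when the daily log ends. Section 6.1 says "Subjects will discontinue daily logs and measures after the third mepolizumab visit (Visit 7"), and the Table 1 footnote agrees. Section 7.1.3 says "The daily logs and measures will be completed through the end of study endpoint assessments (Visit 8").

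Section 15.1 models the maximum daily score per cycle with a fixed person effect, and its simulation gives every subject four cycles. Neither 15.1 nor 15.2 says what to do with missing cycles or with cycles after rescue.

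**The concern.** The daily log feeds the primary endpoint. If a subject who is not responding is taken off study after one or two doses and stops logging, the cycles that are lost are the ones showing no benefit. With a separate effect for each person, weight on the common reduction depends on how many post-treatment cycles the person supplies, so the estimate then leans on the responders.

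This matters because 15.1 intends the 95% confidence interval to support claims beyond a difference from zero, with a reduction of at least 30% as its example. The size of the estimate is therefore part of the result. In an uncontrolled study with 5 to 12 treated subjects, one person can move it.

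**Working it through.** **1. The plan's own figures.** Simulating the 15.1 model (n = 5, four cycles, person mean gamma with mean 3 and variance 3, extra variation gamma with mean 1 and variance 0.25, dispersion not below 1, t with 20 − 6 = 14 degrees of freedom) gives:
- power at 87.5% reduction: 91.1% (plan: over 91%);
- intervals showing at least a 30% reduction: 80.1% (plan: 80%);
- two-sided type I error: 4.7% (plan: 4.9%);
- one-sided type I error: 3.3% (plan: 3.4%).

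**2. Cycles at stake.** On Table 1's 4-week schedule the first dose is Day 15, Visit 7 is Day 71 and Visit 8 is Day 99. Logs to Visit 8 cover 99 − 15 = 84 days, three 28-day cycles. Logs to Visit 7 cover 71 − 15 = 56 days, two cycles.

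**3. How weight is lost.** Let k be a subject's number of post-treatment cycles, P the post-treatment total, T the overall total, and R one minus the reduction. The estimate solves Σ[P − T·kR/(1 + kR)] = 0. Assume a baseline peak of 3, responders at 87.5% reduction and non-responders at 0%. These response figures, and the numbers of non-responders below, are assumptions.

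One non-responder of 5, three cycles each:
- A responder has P = 3 × 3 × 0.125 = 1.125 and T = 4.125. The non-responder has P = 9 and T = 12.
- ΣP = 4 × 1.125 + 9 = 13.5 and ΣT = 4 × 4.125 + 12 = 28.5, so 3R = 13.5/(28.5 − 13.5) = 0.9 and R = 0.30. The reduction is 70.0%.
- The non-responder's weight is 12/28.5 = 42%.

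If that subject leaves after one cycle, P = 3, T = 6 and k = 1:
- The equation is 7.5 = 16.5 × 3R/(1 + 3R) + 6R/(1 + R), so R = 0.214. The reduction is 78.6% and the subject's weight is 18%.

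**4. Every non-responder stopped (expected values).**

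| Non-responders | Complete | Exit after 2 cycles, log to Visit 8 | Exit after 1 cycle, log to Visit 8 | Exit after 1 cycle, log to Visit 7 |
|---|---|---|---|---|
| 1 of 5 | 70.0% | 73.2% | 78.6% | 76.1% |
| 2 of 5 | 52.5% | 56.5% | 65.5% | 61.3% |
| 1 of 12 | 80.2% | 81.9% | 84.3% | 83.2% |
| 2 of 12 | 72.9% | 75.8% | 80.4% | 78.3% |
| 5 of 12 | 51.0% | 55.1% | 64.2% | 60.0% |

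With logs to Visit 8 the shift is 2 to 4 points after two cycles and 4 to 13 after one. With logs to Visit 7 it is 3 to 9 points after one cycle, and exit after two loses nothing.

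**5. Exit driven by the data.** Suppose a subject leaves only when the baseline peak is above 0 and the first post-treatment peak is at or above it. Simulated medians, complete versus exit:
- 1 of 5: 70.8% vs 73.7%;
- 2 of 5: 53.3% vs 55.9%;
- 1 of 12: 80.3% vs 82.0%;
- 2 of 12: 73.1% vs 75.8%.

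That is about 2 to 3 points, and 0 to 1 if two such cycles are required. A variant that also lets subjects with a zero baseline exit gives somewhat more: 71% to 75% for 1 of 5 and 52% to 58% for 2 of 5.

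**6. Effect on inference.**
- Intervals wholly above 30% reduction, data-driven exit: 41.1% vs 40.9% (1 of 5) and 82.6% vs 83.7% (2 of 12).
- The same, with every non-responder stopped after one cycle: 39.6% vs 48.2% (1 of 5) and 82.1% vs 90.0% (2 of 12).
- Significant result with one non-responder stopped after one cycle: 62.9% vs 68.9% (n = 5) and 99.2% vs 99.5% (n = 12).
- Common 87.5% effect, data-driven exit: median 87.9% vs 87.9% (n = 5) and 87.5% vs 87.6% (n = 12).
- No effect in anyone, data-driven exit: false claim of a reduction 3.3% vs 3.1% (n = 5) and 3.7% vs 3.6% (n = 12).

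**The case against.** The strongest reply is that the protocol does not intend efficacy exits before Visit 8. All subjects are due three doses, benefit is judged at Visit 8, and those without benefit finish there. Section 12.8 does not name lack of efficacy, so that route runs only through its best-interest clause. Falling doses make the de-escalation phase a natural place for such an exit, and there it costs the primary model nothing. This stands as a description of the expected path, and it makes the harm conditional. But those statements do not limit 6.6, which covers the whole study.

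The second reply concerns size. With data-driven exit, one simulation gave a median estimate and median interval of 70.4% (20 to 89) complete against 73.3% (20 to 91) with exit for 1 of 5, and 73.7% (52 to 86) against 76.3% (54 to 88) for 2 of 12. A shift of about 3 points inside intervals that wide will rarely change how a proof-of-principle pilot is read. That also stands, and it is why this is an improvement to the estimate and no more.

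Three stronger readings are tempting and not supported:
- A reader might infer that nothing but reasons and safety labs is collected at exit. The opening of 6.6 also provides a clinical assessment for subjects who choose to withdraw. What is missing is the daily log.
- A reader might infer that the test is invalid. The null simulations show no material inflation.
- A reader might take 13 points as the expected bias. It needs every non-responder to be stopped after one cycle, and about 40% of subjects not to respond (2 of 5 or 5 of 12). The documents say neither.

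**Conclusion.** The concern holds in a limited form. Section 6.6 permits a lack-of-efficacy exit before Visit 8, no section keeps the log going, and Section 15 has no rule for incomplete cycles. If response differs between subjects and non-responders are stopped early, the average percent reduction is overstated. With assumed reductions of 87.5% and 0%, the size is about 3 points under a data-driven exit after one cycle, and 4 to 13 points if every non-responder leaves after one cycle with logs otherwise running to Visit 8. It is near zero under a common effect, and false claims of a reduction do not rise materially. The conflict over the log's end date is a separate defect. It matters here because it decides whether two or three post-treatment cycles can be lost.

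**What to change.** 1. In 6.6, state that stopping mepolizumab for lack of efficacy before Visit 8 does not end data collection, and that dosed subjects who agree continue the REDCap daily log to Visit 8. The decision on when to stop treatment is unchanged.
2. Align the log end date in 6.1 and the Table 1 footnote (Visit 7) with 7.1.3 (Visit 8).
3. In 15.2, state that all dosed subjects and all logged cycles are analysed, with a sensitivity analysis that leaves out cycles after rescue or a corticosteroid increase.

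Do not fill missing or rescued cycles with the baseline value. It looks conservative but is not. Subjects who trigger exit tend to have drawn a low baseline, and filled values carry no variation. With no true effect and exit on the first post-treatment peak, filling moves the median reduction to about +5 to +6% and raises false claims to 4.8% (n = 5) and 6.6% (n = 12), against 3.4% and 3.7% with complete data.

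The cost is a few sentences and slightly more remote log entry for a few subjects. One weakness remains: cycles after rescue may still flatter mepolizumab in the all-cycles analysis, since Section 1.1 says "Although conventional HES therapies, including glucocorticoids, are effective in reducing symptoms". For 1 of 5 with two rescued cycles and an assumed 75% rescue effect, ΣP = 4.5 + 3 + 2 × 0.75 = 9, so 3R = 9/15, R = 0.20 and the estimate is 80.0%. Leaving those cycles out gives 78.6%, and neither recovers the 70.0% of complete unrescued data. The requirement in 8.1.2 to hold corticosteroids steady should keep such cycles few.
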